14.7.1 Incomplete Start Date

The following rules will be applied to impute the missing numeric fields for an incomplete prior or concomitant medication start date.

Missing month and day

- If the year of the incomplete start date is the same as the year of the first dose of randomized IP, the month and day of the first dose of randomized IP will be assigned to the missing fields.
- If the year of the incomplete start date is before the year of the first dose of randomized IP, 31 Dec will be assigned to the missing fields.

- If the year of the incomplete start date is after the year of the first dose of randomized IP, *01 Jan* will be assigned to the missing fields.

Missing month only

- If only the month is missing, the day will be treated as missing and both the month and the day will be replaced according to the above procedure.

Missing day only

- If the month and year of the incomplete start date are the same as the month and year of the first dose of randomized IP, the day of the first dose of randomized IP will be assigned to the missing day.
- If either the year of the incomplete start date is before the year of the date of the first dose of randomized IP or if both years are the same but the month of the incomplete start date is before the month of the date of the first dose of randomized IP, the last day of the month will be assigned to the missing day.
- If either the year of the incomplete start date is after the year of the date of the first dose of randomized IP or if both years are the same but the month of the incomplete start date is after the month of the date of the first dose of randomized IP, the first day of the month will be assigned to the missing day.

14.7.2 Incomplete Stop Date

The following rules will be applied to impute the missing numeric fields for an incomplete prior or concomitant medication stop date. If the imputed stop date is before the start date (imputed or nonimputed start date), the imputed stop date will be equal to the start date.

Missing month and day

[figure not shown]
- If the year of the incomplete stop date is the same as the year of the last dose of randomized IP, the month and day of the last dose of randomized IP will be assigned to the missing fields.
- If the year of the incomplete stop date is before the year of the last dose of randomized IP, *31 Dec* will be assigned to the missing fields.
- If the year of the incomplete stop date is after the year of the last dose of randomized IP, *01 Jan* will be assigned to the missing fields.

[figure not shown]
Missing month only

- If only the month is missing, the day will be treated as missing and both the month and the day will be replaced according to the above procedure.

Missing day only

- If the month and year of the incomplete stop date are the same as the month and year of the last dose of randomized IP, the day of the last dose of randomized IP will be assigned to the missing day.
- If either the year of the incomplete stop date is before the year of the date of the last dose of randomized IP or if both years are the same but the month of the incomplete stop date is before the month of the date of the last dose of randomized IP, the last day of the month will be assigned to the missing day.
- If either the year of the incomplete stop date is after the year of the date of the last dose of randomized IP or if both years are the same but the month of the incomplete stop date is after the month of the date of the last dose of randomized IP, the first day of the month will be assigned to the missing day.

[figure not shown]

RESERVED

15.0 CHANGES TO ANALYSES SPECIFIED IN PROTOCOL

This SAP amendment includes additional analyses listed below. There are no other changes to the analyses specified in the final Protocol Amendment 2 (version dated 12 Oct 2018) and Amendment 3 (version dated 20NOV2018).

- Prior ADT use in current episode recorded on ATRQ (Section 7)
- Weight adjusted dose of rapastinel (section 8.4)

RESTRICTED

17.0 APPENDICES

RESTRUCTURED

RESTRICTED

APPENDIX II. PATTERN-MIXTURE MODEL DETAILS

For repeated measures under monotone missing, the pattern-mixture model with non-future dependent missing assumption proposed by Kenward et al (2003) provides a feasible solution to accommodate certain missing not at random (MNAR) mechanism. The methodology relies on constructing unidentifiable conditional densities using identifiable densities and borrows techniques from standard multiple imputation.

1. Non-Future Dependent Missing Assumption

Assume there are T designed visits in a longitudinal study and let y_i ($i = 1, 2, \dots, T$) represent patient's measurement at Visit i . When the missing is monotonic, the pattern of missing *data* can be defined by the number of measurements (L) actually observed from the patient. Let $f(y_1, \dots, y_T | L = t)$ denote the conditional density of y_1, \dots, y_T , given **that** the last observed measurement at Visit t . Then the overall density function for Pattern t can be written as

$$f(y_1, \dots, y_T | L = t) = f(y_1, \dots, y_t | L = t) f(y_{t+1} | y_1, \dots, y_t, L = t) \times \prod_{s=t+2}^T f(y_s | y_1, \dots, y_{s-1}, L = t) \quad (1)$$

Note on the right hand side of (1) the first factor is clearly identifiable from the observed data, while the second and the beyond are not, due to lack of available data. The second factor $f(y_{t+1} | y_1, \dots, y_t, L = t)$ could be identifiable based on an assumed relationship between $f(y_{t+1} | y_1, \dots, y_t, L = t)$ and $f(y_{t+1} | y_1, \dots, y_t, L \geq t + 1)$. The third and beyond factors $f(y_s | y_1, \dots, y_{s-1}, L = t)$ (with all $s \geq t + 2$) could be identifiable with the help of non-future dependent missing assumption.

For longitudinal data with dropouts, non-future dependent missing (NFD) (Kenward, 2003) assumes that the unidentifiable conditional distributions of y_s ($s \geq t + 2$), *given earlier measurements*, in Pattern t , *is set to be equal to the corresponding distribution in pattern $L > s-1$* :

$$f(y_s | y_1, \dots, y_{s-1}, L = t) = f(y_s | y_1, \dots, y_{s-1}, L \geq s - 1) \quad (2)$$

The right hand side of (2) can further be partitioned into

$$f(y_s | y_1, \dots, y_{s-1}, L \geq s - 1) = \sum_{j=s-1}^T \omega_{s-1,j} \cdot f(y_s | y_1, \dots, y_{s-1}, L = j) \quad (3)$$

where mixture probabilities $\omega_{s-1,j}$ are

$$\omega_{s-1,j} = \frac{\alpha_j f(y_1, \dots, y_{s-1} \mid L = j)}{\sum_{t=s-1}^T \alpha_t f(y_1, \dots, y_{s-1} \mid L = t)}, \text{ and } \alpha_j \text{ represents the fraction of patients from Pattern } j. \quad (4)$$

Each factor of the unidentifiable conditional distribution of y_s ($s \geq t + 2$) on the right side of (1) can be expressed using the following:

- $f(y_s \mid y_1, \dots, y_{s-1}, L = s - 1)$, the unidentifiable conditional distribution of the first missing in pattern $s-1$,
- $f(y_s \mid y_1, \dots, y_{s-1}, L = j)$, the identifiable conditional distributions of y_s given y_1, \dots, y_{s-1} of pattern j ($j \geq s$), and
- α_j , the fraction of patients from pattern j ($j \geq s - 1$).

So under NFD, all the unidentifiable conditional distributions on the right side of (1) can be estimated and missing values could be therefore imputed based on the assumption for unidentifiable conditional distribution of the first missing *value*.

We re-formulate the partition in (3), for $s \geq t + 2$, as the following:

$$f(y_s \mid y_1, \dots, y_{s-1}, L = t) = \delta_{s-1} f(y_s \mid y_1, \dots, y_{s-1}, L = s - 1) + (1 - \delta_{s-1}) f(y_s \mid y_1, \dots, y_{s-1}, L \geq s) \quad (5)$$

for $s \geq t + 2$ with $\delta_{s-1} = \omega_{s-1,s-1}$.

Therefore, under monotone missing and NFD assumption, the unidentifiable conditional densities for Visit s in Pattern t ($s \geq t + 2$) can be expressed as a mixture distribution of $f(y_s \mid y_1, \dots, y_{s-1}, L = s - 1)$ - the unidentifiable conditional distribution of the first missing measurement y_s in Pattern $s - 1$, and $f(y_s \mid y_1, \dots, y_{s-1}, L \geq s)$ - the identifiable conditional distribution of y_s from all the patterns with observed data at Visit s or beyond:

$$f(y_s \mid y_1, \dots, y_{s-1}, L \geq s) = \sum_{j=s}^T \lambda_{s-1,j} f(y_s \mid y_1, \dots, y_{s-1}, L = j) \quad (6)$$

where the mixture probability

$$\lambda_{s-1,j} = \omega_{s-1,j} / (1 - \omega_{s-1,s-1}) =$$

$$\frac{a_j f(y_1, \dots, y_{s-1} | L = j)}{\sum_{t=s}^T a_t f(y_1, \dots, y_{s-1} | L = t)} \text{ for } j \geq s, \text{ where } a_j \text{ is the fraction of } \\ (7)$$

patients from Pattern j .

The conditional densities for the first missing are selected as:

$$f(y_s | y_1, \dots, y_{s-1}, L = s-1) = f(y_s - \Delta | y_1, \dots, y_{s-1}, L \geq s) \text{ for } s = 2, \dots, T, \quad (8)$$

Note that the two distributions only differ from a shift (Δ) parameter. When $\Delta = 0$, the missing value y_s in Pattern $s-1$ is imputed based on the distribution of all observed data up to Visit s , as a result, leading to missing at random (MAR) missingness. When $\Delta \neq 0$, (8) will introduce a scenario of MNAR. A similar idea was also presented in the recent publication “*The Prevention and Treatment of Missing Data in Clinical Trials*” by the National Academy Press. The selection of the plausible values for the shift parameter (Δ) is discussed in Section 3.

Note that per recommendation in Wang and Daniels (2011), only the observed data within the pattern is assumed to be multivariate normal. The observed data distribution can be expressed in terms of the marginal distribution of baseline measurements and the conditional distributions of postbaseline measurements given earlier measurements. Assuming that these distributions are normal, the linear regression of each observation on prior observations will yield least-squares estimates of model parameters that can be utilized for independent posterior draws of model parameters for observed data. The multiple imputation approach will be used to estimate the overall mean at the final time point.

2. Imputation Procedure

All the missing data will be imputed to create a complete dataset, then statistical analysis can be performed using appropriate techniques such as **MMRM**. The imputation **can accommodate** MNAR **missing data mechanisms**, based on the theory discussed in the above sections.

The model parameters for each dropout pattern, i.e., the mean, variance and proportions of observations in each pattern, are drawn from their posterior distributions prior to the imputation of missing data for a single imputation.

The details of imputation within a pattern, say Pattern t , are as the following:

Step 1. Impute the first missing value y_{t+1} for each patient in Pattern t ($t = 1, \dots, T-1$):

- a. Compute estimates of mixture probabilities $\lambda_{s-1,j}$ in (7) with $s = t+1$ given the posterior draw of proportions of observations in each pattern and the posterior draw of regression parameters for the observed data.
- b. Draw a random integer from $\{s, \dots, T\}$ to index a component distribution on the right hand side of (6), using mixture probabilities obtained in a). Draw y_{t+1}^* from the identified component normal distribution. Impute the missing y_{t+1} as $\tilde{y}_{t+1} = y_{t+1}^* + \Delta$.

Step 2. Impute the rest of the missing values of $y_{t+2}, y_{t+3}, \dots, y_T$ for patients in Pattern t:

Starting with imputation for y_{t+2} , first, similar to Step 1, draw y_{t+2}^* from the normal mixture (6) based on the observed y_1, \dots, y_t and the already imputed \tilde{y}_{t+1} for the patient. Then the missing y_{t+2} is imputed as $\tilde{y}_{t+2} = y_{t+2}^* + \Delta$ with probability δ_{t+1} and as $\tilde{y}_{t+2} = y_{t+2}^*$ with probability $1 - \delta_{t+1}$, where the mixture probability $\delta_{t+1} = \omega_{t+1,t+1}$ is obtained from (4) given the posterior draw of proportions of observations in each pattern and the posterior draw of regression parameters for the observed data.

Missing values of y_{t+3} through y_T can be imputed similarly as y_{t+2} .

To summarize, the imputations of y_{t+1} through y_T is done recursively within each Pattern t (for all $t = 1, \dots, T - 1$) to create a complete dataset after imputation is done for all patterns with missing values.

The above imputation procedure is applied to all subjects in each missing data pattern to create a single imputed data set. Repeating the process of drawing parameters from the posterior distribution and imputing missing data given the posterior draw m times will yield m imputed data sets. The observed or imputed values at the final data point are averaged to obtain the overall mean estimate for each imputed data set, and the multiple imputation estimate is obtained by averaging the estimates across m imputations.

In this sensitivity analysis, m is set to equal to 20. The value of m is discussed in the context of imputation efficiency in standard multiple imputation theory (Rubin, 1987, p. 114), and $m = 20$ would provide at least 96% of relative efficiency as compared with using a large number of imputations (SAS/STAT User's Guide, p. 3796).

3. Determination of the Shift Parameter Values

The common shift parameter Δ is the difference between the mean of y_{t+1} among those who drop out at Visit t and those who remain beyond Visit t ($1 \leq t \leq T - 1$). The exact value of Δ is unknown and can't be estimated from data because of missingness. The magnitude of Δ depends on the medical aspects of the trial. Using relevant historical data, one may select Δ as a proportion of the sample standard deviation or a proportion of observed treatment efficacy.

RESTRICTED

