To assess the robustness of the primary MMRM results to the possible violation of the missing-at-random assumption, a sensitivity analysis using a pattern-mixture model based on non-future dependent missing value restrictions (Kenward et al, 2003) will be performed. The pattern for the pattern-mixture model will be defined by the patient's last visit with observed value. The observed MADRS total score at a visit is assumed to have a linear relationship with the patient's prior measurements. The missing values will be imputed under the assumption that the distribution of the missing observations differs from the observed only by a shift parameter value Δ . The dataset with missing values will be analyzed using the same model as the primary analysis for between-treatment group comparisons. The imputation of missing values and the analysis will be performed multiple times and the inference of this sensitivity analysis will be based on the combined estimates using the standard multiple imputation technique. The values for Δ will be selected as 0 to 8.

[figure not shown]

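### As written, the missing-data sensitivity analysis imputes MADRS scores without a treatment term, so its Delta = 0 run does not make the primary MMRM's missing-at-random assumption and pulls the treatment difference slightly toward zero

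*SAP*

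**What the plan says.** SAP 8.1 plans one pattern-mixture analysis to test the primary result against departures from missing at random. Patterns are defined by the last visit with an observed score, and the imputation model is described in one sentence: "The observed MADRS total score at a visit is assumed to have a linear relationship with the patient's prior measurements". Protocol 9.7.5.1 has the same description. The completed data are to be "analyzed using the same model as the primary analysis for between-treatment group comparisons". In SAP 8.1 that model includes treatment group, treatment-by-visit, responder status, pooled centre, and the Day 0 and baseline scores with their visit interactions.

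Appendix II gives the algorithm. Its densities (1) to (8) condition on earlier scores and dropout pattern, and the parameters come from a regression on earlier scores: "the linear regression of each observation on prior observations will yield least-squares estimates of model parameters". On scope it says: "The above imputation procedure is applied to all subjects in each missing data pattern to create a single imputed data set". Of Delta = 0 it says the imputation uses all observed data up to the visit, "as a result, leading to missing at random (MAR) missingness". The stated target is a single mean: "The multiple imputation approach will be used to estimate the overall mean at the final time point". No step mentions treatment, responder status or centre.

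**The concern.** An imputation model that leaves out the factor being tested tends to give the missing patients of both arms similar values. The arm difference among imputed patients is then smaller than among observed ones, and the overall difference is diluted. The dilution is partial, because earlier post-randomization scores carry some of the treatment effect forward.

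The Delta series is meant to show how far the result moves as the missing-at-random assumption is relaxed. That reading is clean only if the series starts close to the primary analysis. The MMRM's assumption is missing at random given treatment, covariates and past scores. The assumption written in Appendix II is missing at random given past scores alone. Part of any gap between the Delta = 0 result and the primary result would then come from the omitted term and not from the missing data. This is the only missing-at-random sensitivity analysis described for the primary endpoint in the visible text.

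**Working it through.** **The plan's own figures.** None bears directly on this point, so I first checked the sample-size inputs reused below. For 350 per arm, difference 3.25, SD 10 and two-sided 0.05, power is Φ(3.25/(10·√(2/350)) − 1.96) = 0.990, matching the stated 99%. For the revised size, 2·(1.96 + 1.28)²·8.7²/3.25² gives 151 per arm, 302 in total. Then 302/0.85 = 356, against the stated 360. The 3.25 is assumed here, because Protocol 9.7.9 and SAP 12.0 state it only for the original one-day endpoint.

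**Inputs.**
- SD 8.7, correlation 0.5, 210 per arm and 10% dropout in the randomized period, with under 5% overall reported (SAP 12.0).
- Baseline and six later visits, Days 8, 11, 14, 15, 18 and 21 (SAP Table 14.1–2), which gives five dropout patterns.
- My assumptions: Day 21 difference 3.25; the same correlation between all visits; dropout unrelated to outcome and spread evenly over visits; Delta = 0.

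**Method.** With the arms combined 1:1 and treatment ignored, the covariance seen by the regression is M = Σ + ¼·d·dᵀ, where d holds the treatment differences by visit (zero at baseline). Imputed values for a dropout carry only the difference transmitted through the slopes on earlier scores. If g_t is the Day 21 difference carried by patients last seen at visit t, and w_t is their share, the shrinkage is Σ w_t·(3.25 − g_t).

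**One case by hand.** Take a constant effect and a patient last seen at Day 8. Variances are 75.69 at baseline and 75.69 + 2.64 = 78.33 at Day 8. The covariance with baseline is 37.85, and between post-baseline visits it is 37.85 + 2.64 = 40.49. The slope on the Day 8 score is (75.69 × 40.49 − 37.85²)/(75.69 × 78.33 − 37.85²) = 0.363. The carried difference is 0.363 × 3.25 = 1.18 points instead of 3.25.

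**All cases.**

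| Effect over visits | g_t, last seen Day 8, 11, 14, 15, 18 | Shrinkage at 5% (estimate) | Shrinkage at 10% (estimate) |
|---|---|---|---|
| Constant 3.25 | 1.18, 1.73, 2.05, 2.26, 2.41 | 0.07 (3.18) | 0.13 (3.12) |
| Growing linearly to 3.25 | 0.19, 0.42, 0.68, 0.96, 1.25 | 0.13 (3.12) | 0.26 (2.99) |
| Last visit only | 0 throughout | 0.16 (3.09) | 0.33 (2.93) |

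The last row is the ceiling for these profiles, dropout × 3.25: 0.05 × 3.25 = 0.16 and 0.10 × 3.25 = 0.33.

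**Simulation.** Sequential-regression multiple imputation with 40,000 per arm and arms combined gave 3.18, 3.12 and 3.09 at 5%, and 3.09, 2.97 and 2.90 at 10% (Monte Carlo standard errors 0.012 to 0.016). Run within arm, it gave 3.22 to 3.25 throughout. With 210 per arm at 10% the combined run gave 3.14, 2.99 and 2.92 (standard errors about 0.06). Across these runs the shrinkage at 10% is 0.11 to 0.35.

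**Scale.** The unadjusted standard error of the difference is 8.7·√(2/210) = 0.85 points. At 5% dropout the shrinkage is 0.07/0.85 = 0.08 to 0.16/0.85 = 0.19 of a standard error.

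**Limits of the check.** The regressions combine dropout patterns instead of drawing from mixture (6), and the simulation ends with an ANCOVA at Day 21, not the full MMRM.

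**The case against.** The strongest reply is that Appendix II is a generic one-sample exposition. Its target is one overall mean, whereas SAP 8.1 requires a comparison between groups, so the appendix cannot be the whole algorithm, and running it within each arm is a natural completion. This stands in part. A reader might infer that the sponsor will in fact impute from both arms combined. The documents do not say so, and applying the procedure to all subjects in each pattern need not mean merging the arms. But nothing calls for a by-arm run either, and a programmer following the steps literally would combine the arms. The two readings give different answers.

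Second, the SAP says only that Delta = 0 gives missing at random, not that it reproduces the primary MMRM. That is correct, and exact agreement should not be expected. The point is that the assumption as written conditions on less than the primary model does.

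Third, a reader might size the effect at 15% dropout, the overall rate in Protocol 9.7.9. SAP 12.0 places 5% of that in the placebo lead-in, before randomization. Those patients are outside the mITT population (SAP 4.3) and are never imputed here, so 10% is the relevant planning rate.

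Fourth, Appendix II closes with "The observed or imputed values at the final data point are averaged to obtain the overall mean estimate for each imputed data set", which a reader might take as a contradiction of SAP 8.1. It is largely settled by SAP 8.1 and by Appendix II itself, which names MMRM as a technique for the completed data. It needs only a wording change.

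**Conclusion.** The point holds for the text as written. The imputation omits treatment, the analysis model includes it, and on the literal reading the Delta = 0 estimate is pulled toward zero by about 0.07 to 0.16 points at 5% dropout and about 0.13 to 0.33 at 10%. These sizes rest on the assumed 3.25-point Day 21 difference, SD 8.7, a common correlation of 0.5 and dropout unrelated to outcome. They scale with dropout and with how late the effect emerges.

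A reader might infer that the sensitivity analysis is unusable, or that a loss of significance in it would say nothing about missing data. The figures do not support that: at the reported dropout of under 5% the shift is below a fifth of a standard error. Nor does the flaw favour rapastinel, since at Delta = 0 it works against a difference and cannot by itself make the result look robust. It is a modest specification fault that is cheap to correct.

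**What to change.** In SAP 8.1 and Appendix II:

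- Include randomized treatment as a predictor in each visit's imputation regression, preferably with the Day 0 score and responder status that the primary model uses.
- State how sparse dropout patterns are merged. Fewer than 5% of about 420 is fewer than 21 dropouts; over five patterns that is about 4 each, or about 2 per pattern per arm. Within-pattern regressions are already tight at that size, which is why a treatment term is easier to support than fully separate models by arm.
- Add a check that the Delta = 0 estimate approximates the primary MMRM estimate. It will not reproduce it exactly, because a mixture over patterns is not the same model and pooled centre would still be absent.
- Reword the averaging sentence in Appendix II so that the completed data go to the primary model, as SAP 8.1 requires.

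The cost is slightly more programming and some extra parameters in sparse patterns, which the merging rule handles.
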